## Statistical Analysis Plan

### Version history

Version number	Version date	Prepared/reviewed by	Description of the changes made
1	7/30/23	[name] [name]	Original

### Study Aims

**Overall objective:** Assess the acceptability and side effects of consuming dried moringa leaf powder (MLP) at 3 different doses (1, 2, or 3 teaspoons) daily for 7 days, among UC Berkeley staff employees.

**Specific Aim 1:** Describe the total acceptability score of MLP, and whether it differed by dose group.

**Sub-Aim 1.1:** Describe the average scores for liking the taste, texture, and appearance of foods after adding MLP, and determine whether they differed by the dose group.

**Specific Aim 2:** Describe the total number of days MLP was consumed during the 7-day intervention period, and whether it differed by the assigned dose.

**Specific Aim 3:** Describe the proportion of participants who reported gastrointestinal or other symptoms after consuming MLP and determine whether it differed by dose group.

**Secondary Aim 1:** Describe the rate of reported willingness to continue consuming MLP and whether it differed by dose group.

**Secondary Aim 2:** Determine the average number of teaspoons consumed (daily and total) for each dose group, based on available data (daily consumption reports), and whether the proportion of the assigned dose consumed differed by group.

**Secondary Aim 3:** Determine whether skin carotenoid score (SCS) increased after consuming MLP for one week, and whether the change in SCS differed by dose group.

### Study Design and Sample

The study design is an unblinded, randomized controlled trial in which UC Berkeley (non-student) staff members volunteered to be randomly assigned to consume 1, 2, or 3 teaspoons of MLP every day for 7 days. We did not include a control group in order to maximize the sample size for the main outcome of interest, which was the acceptability of consuming moringa.

The analytical samples will differ for each aim based on the outcome data source (daily surveys or final interview), and will include those with available data. See Analysis Principles below for further details on the modified intention-to-treat approach.

### Variables

#### **Exposure:**

**Daily consumption of 1, 2, or 3 teaspoons MLP added to foods or drinks for one week.** Total doses of 7, 14, or 21 teaspoons of MLP were provided to participants to take home at the beginning of the study

(day 1), and compliance was measured by questions asked on daily online surveys and the final interview. For main analyses, the exposure will be defined as the intervention group to which the participant was assigned at the beginning of the study.

**Outcomes:**

- **Acceptability.** On day 8 of the study, 3 aspects of acceptability (taste, texture, and appearance) of foods or drinks after adding MLP were assessed using a 5-point liking scale, where a reported value of 1 indicated “Dislike it a lot”, 2 indicated “Dislike it a little”, 3 indicated “Neither like nor dislike”, 4 indicated “Like it a little”, and 5 indicated “Like it a lot”. The text descriptions and numbers were accompanied by emoji faces representing the corresponding level of like or dislike. *Total acceptability scores* will be calculated by summing the 3 *sub-scores*, with a potential range of 3-15 points.
- **Consumption.** The *total number of days consuming MLP* during the intervention period will be assessed using the following question asked at the final interview (day 8): “During the past week, how many days did you consume moringa powder?”. The *average daily dose* (tsp) consumed will be defined as the mean quantity reported consumed among days where consumption data is available. Among participants with available daily consumption data for  $\geq 4$  of the 7 intervention days, the total amount (tsp) of MLP consumed during the intervention period will be calculated by multiplying the reported number of days consumed by the average reported amount consumed on consumption days. To measure the degree of compliance, this total will be divided by the total assigned dose and multiplied by 100 to obtain the *percent of the assigned dose consumed*.
- **Willingness to continue consuming MLP.** At the final interview (day 8), participants were asked about their *willingness to continue consuming MLP* using the question, “Would you be willing to continue taking the moringa powder?”. Response options included “yes”, “no”, or “not sure”.
- **Symptoms.** Gastrointestinal and other symptoms experienced in the previous 24 hours were assessed on day 1 of the study via the baseline interview, on days 2-7 via the daily survey, and on day 8 via the final interview. Participants were asked whether or not they had experienced diarrhea, bloating, stomach ache, other digestive problems, allergic reactions (e.g. rash, hives, fever, difficulty breathing, low blood pressure, etc.), or other symptoms. The *proportion of participants who reported any symptoms* will be calculated. The *total number of symptoms experienced* will be described as the total number of different symptoms (e.g. diarrhea + bloating = 2 symptoms) reported, 1) on each day, and 2) during the whole intervention period.
- **Skin carotenoid level.** Skin carotenoid level was assessed on study days 1 and 8 using the Veggie Meter®, a commercially available reflection spectrometry device that outputs a skin carotenoid score (SCS) between 0 and 800, which is correlated with dietary intake of fruits and vegetables. Skin carotenoid levels were measured in triplicate and averaged by the Veggie Meter® software. The *change in SCS* will be calculated by subtracting each participant’s baseline SCS from their SCS at the final interview.

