### Baseline participant characteristics

Descriptive summary statistics for sociodemographic and other variables will be reported overall and by intervention group. Age and baseline skin carotenoid scores will be summarized as mean (SD) or median (IQR). Gender identity, racial/ethnic identity, and gastrointestinal and other symptoms (any, as well as individual symptoms) reported by participants in the last 24 hours at baseline will be reported as frequency (%).

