### Primary Analyses

**Aim 1 (Acceptability):** Distributions of total acceptability scores and sub-scales will be presented as mean (SD) or median (IQR). We will investigate average differences between the 3 intervention groups in total acceptability scores and sub-scores using one-way ANOVA, Welch's ANOVA or Kruskal Wallis tests.

**Aim 2 (Consumption):** We will present the proportion of participants who reported consuming MLP for the full 7 days vs. less, as well as the proportion of participants reporting each frequency of consumption (e.g. 5 days, 6 days, etc.) and/or the mean (SD) or median (IQR) number of days consumed. All descriptive statistics will be reported overall and by intervention group. To investigate whether the number of days differed by intervention group, we will conduct Kruskal-Wallis tests.

**Aim 3 (Symptoms):** The proportion of participants reporting symptoms (any, as well as individual symptoms) during the intervention period will be reported overall (whole intervention period) and by study day for each group. The total number of symptoms reported will be presented in a similar manner. In addition, line graphs will be generated to visualize individual participant trajectories in terms of the number of symptoms reported each day and response/non-response to the daily surveys, and will be color-coded by assigned dose to visualize trends by group. Chi-square or Fisher's Exact test will be used to test whether the frequency of reporting any symptoms differed by assigned dose. ANOVA, Welch's ANOVA or Kruskal-Wallis tests will be used to test whether the total number of reported symptoms differed by dose group.

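### Aim 3 makes no participant-level use of the pre-dose symptom report, so a complaint already present on day 1 and repeated later counts as a symptom after MLP

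*SAP*

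**What the plan says.** The overall objective is to "Assess the acceptability and side effects of consuming dried moringa leaf powder (MLP) at 3 different doses". Specific Aim 3 is to "Describe the proportion of participants who reported gastrointestinal or other symptoms after consuming MLP and determine whether it differed by dose group". Under Study Design and Sample the SAP states "We did not include a control group in order to maximize the sample size for the main outcome of interest", so the trial has no concurrent background symptom rate.

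Under Outcomes (Symptoms), symptoms over the previous 24 hours "were assessed on day 1 of the study via the baseline interview", then by daily survey on days 2 to 7 and at the final interview on day 8. That makes eight reports. Under Exposure, the supplies of powder "were provided to participants to take home at the beginning of the study", so the day-1 report is pre-dose.

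The baseline section says that symptoms "reported by participants in the last 24 hours at baseline will be reported as frequency", overall and by group. For Aim 3, the Primary Analyses section says: "The proportion of participants reporting symptoms (any, as well as individual symptoms) during the intervention period will be reported overall" and by study day for each group. Any symptom is then tested by dose with a chi-square or Fisher's exact test, and the number of symptoms with ANOVA, Welch's ANOVA or Kruskal-Wallis. No Aim 3 analysis uses the day-1 report as an exclusion, a change measure, a covariate or a sensitivity analysis.

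**The concern.** The aim is about symptoms that follow consumption, and the objective calls them side effects. The planned measure is any symptom reported in the period, whether or not the participant already had it. With no untreated group, the participant's own pre-dose report is the only information in the trial on what that person felt without MLP, and Aim 3 does not use it at that level.

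Two results are affected. The proportions and counts that Aim 3 must describe would include complaints that pre-date the powder. The comparison between doses would carry the same complaints in every group, which narrows any real difference. The SAP treats skin carotenoid score, a secondary outcome, differently: it has a change from baseline and a baseline-adjusted sensitivity model. Symptoms are a primary aim with a baseline measurement and have neither.

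**Working it through.** The SAP gives no symptom rate, sample size or power, so there is no figure to reproduce. The structure follows from the text, and the arithmetic below uses assumed rates only.

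**Step 1: what is counted.** Take a participant who reports bloating on day 1 and on day 3.
- Baseline table: counted once, within the group percentage.
- Aim 3, any symptom: counted as yes, because of day 3.
- Aim 3, number of different symptoms over the period: bloating adds one.
- Nothing in Aim 3 marks the day-3 report as a continuation.

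**Step 2: effect on the proportions.** Let q be the share of participants with a day-1 complaint that recurs on days 2 to 8, and m the share in whom MLP causes a symptom, acting independently. The planned proportion is 1 − (1 − q)(1 − m). With m = 20%:
- q = 5%: 1 − 0.95 × 0.80 = 24%
- q = 10%: 1 − 0.90 × 0.80 = 28%
- q = 20%: 1 − 0.80 × 0.80 = 36%
- q = 30%: 1 − 0.70 × 0.80 = 44%

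**Step 3: effect on the dose comparison.** Assume MLP-caused risks of 10%, 20% and 30% for 1, 2 and 3 teaspoons. The observed 3-versus-1 difference is (1 − q) × 20 points.

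| q | 1 tsp | 2 tsp | 3 tsp | 3 vs 1 difference |
|---|---|---|---|---|
| 0% | 10% | 20% | 30% | 20 points |
| 10% | 19% | 28% | 37% | 18 points |
| 20% | 28% | 36% | 44% | 16 points |
| 30% | 37% | 44% | 51% | 14 points |

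If m is the same in all groups, the observed proportion is also the same in all groups. Randomisation balances q in expectation, so the comparison is diluted and open to chance imbalance, but it is not pushed in one direction.

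**Step 4: what a new-since-baseline count would give.** Take q = 20% and m = 20%. If every MLP-caused symptom in a participant with a baseline complaint is of a different type, the new-symptom proportion is 20%. If it is always of the same type, it is (1 − 0.20) × 0.20 = 16%. The planned figure is 36%. The new-symptom count is thus closer to the assumed 20% but can fall below it, so the two figures should be shown together.

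**The case against.** The strongest reply is that the SAP already separates baseline. Day 1 is labelled the baseline interview, its symptoms have their own table by group, and Aim 3 is limited to the intervention period. A reader might infer that the day-1 report itself is pooled into the Aim 3 measure. The text does not support that. No sentence says which reports make up the intervention period, but that is missing detail rather than an instruction to include day 1. This part of the reply stands.

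Second, baseline proportions by group can be set against the daily proportions by group. This stands for single days. It does not work for the whole-period proportion, where one 24-hour report would be compared with seven, and it cannot show which participants have a new complaint.

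Third, the randomised dose groups are concurrent comparators for the dose question. This stands, and it is why the harm falls mainly on the descriptive figures.

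Fourth, a reader might size the problem by supposing independent background symptoms on each of seven reports. At assumed daily rates of 5%, 10% and 20%, 1 − (1 − p)^7 gives 30%, 52% and 79% with at least one symptom and no effect of MLP. Those figures should not be attached to this point. They measure background arising after baseline, most of which a baseline rule leaves in place. Under the same model, even removing everyone symptomatic on day 1 from the numerator gives 0.302 × 0.95 = 29%, 0.522 × 0.90 = 47% and 0.790 × 0.80 = 63%.

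Finally, reporting all symptoms during use is a defensible choice in a small pilot. That is a reason to keep the all-symptom figure, not a reason to leave the participant-level baseline unused.

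**Conclusion.** The point holds in a limited form. Aim 3 has no participant-level rule for complaints present before the first dose, so a persisting complaint is counted as a symptom after MLP. The descriptive proportions and counts are inflated by an unknown amount. The between-dose test is diluted but not systematically biased.

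The illustrative inflation (from 20% to between 24% and 44%) and the shrinkage of the dose difference (from 20 to between 18 and 14 points) rest on assumed values of q and m and on their independence. Neither is an estimate for this trial. The conclusion also relies on the day-1 report being pre-dose, which follows from when the powder was handed out and from the 24-hour recall.

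This is an inexpensive improvement to a primary aim, not an error that invalidates it. Even after the change, proportions without a control group cannot be read as effects of the powder.

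**What to change.** In the Aim 3 analysis:
- State that day 1 is baseline only and that the reports of days 2 to 8 form the window.
- Beside the all-symptom proportion and count, report symptoms new since baseline, defined as a type not reported on day 1, and test them by dose group with the methods already planned.
- Show the day-1 proportion next to each daily proportion.
- Describe the uncontrolled proportions as symptoms reported during use, not as side effects.

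The cost is a few sentences in the SAP, one derived variable from data already collected, and one further set of comparisons. There are two downsides. A single 24-hour baseline misses intermittent prior symptoms. The type-based rule also does not count as new either a worsening of a symptom or a different complaint within one of the 'other' categories, so it can hide real intolerance. For both reasons the all-symptom figure must stay.

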**Sociodemographic variables**

Sociodemographic variables (for reporting sample characteristics) include *age* (years), *gender* (Man, Woman, Non-binary, or Other), *Latinx/Hispanic ethnicity* (Yes or No), and *racial/ethnic identity* (White, Black or African American, American Indian or Alaska Native, Asian, Native Hawaiian or Pacific Islander,

PI: [name]  
University of California, Berkeley

Mixed, or Other). For gender, all respondents reported identifying as a man or a woman, so this variable will be analyzed as binary. For racial/ethnic identity, responses from the two questions will be combined to create a single categorical variable, and categories will be collapsed into fewer categories if needed to allow for analysis.

### Analysis principles

- Outcomes will be analyzed based on a modified intention-to-treat approach, in which 1) participants with missing outcome data will be excluded (i.e. no imputation will be done), and 2) one participant who was erroneously assigned to a different group from what the randomization order prescribed will be analyzed according to the dose they actually received and were instructed to consume.
- Distributions of variables will be described using frequencies and percentages, in the case of categorical variables, mean (SD) or median (IQR) for continuous variables, and one or both of these for ordinal or count variables.
- Classic ANOVA, Welch's ANOVA, or Kruskal-Wallis tests to detect group differences of ordinal, count and continuous variables will be selected based on whether the following assumptions are met:
  - The distribution within each group is approximately normal based on visual inspection of the data and normal probability plots (Classic ANOVA, Welch's ANOVA).
  - Group variances are approximately equal, i.e., the ratio of the largest to the smallest variance is  $\leq 1.5^{1,2}$  (Classic ANOVA).
- Chi Square or Fisher's Exact test will be used to analyze differences by intervention group for categorical variables.
- Significance level will be set at 0.05. Hypothesis testing results will be interpreted in conjunction with effect sizes and overall trends in the data.
- *Missing data*: For outcomes measured only at the final survey, observations from participants who did not complete the final interview will be excluded from analysis (e.g. Aim 1). For other outcomes, including those measured by daily surveys, available case analysis (e.g. cases with data at each daily survey) will be conducted.
- *Outliers*: Distributions of continuous variables will be visually inspected for outliers, and potential outliers will be investigated further for input errors or other explanations. If no rationale for removing the observation is identified, non-parametric rank-based methods will be considered and/or sensitivity analyses will be conducted to determine the effect of removing the outlier on the results.

### Baseline participant characteristics

Descriptive summary statistics for sociodemographic and other variables will be reported overall and by intervention group. Age and baseline skin carotenoid scores will be summarized as mean (SD) or median (IQR). Gender identity, racial/ethnic identity, and gastrointestinal and other symptoms (any, as well as individual symptoms) reported by participants in the last 24 hours at baseline will be reported as frequency (%).

### Primary Analyses

**Aim 1 (Acceptability):** Distributions of total acceptability scores and sub-scales will be presented as mean (SD) or median (IQR). We will investigate average differences between the 3 intervention groups in total acceptability scores and sub-scores using one-way ANOVA, Welch's ANOVA or Kruskal Wallis tests.

**Aim 2 (Consumption):** We will present the proportion of participants who reported consuming MLP for the full 7 days vs. less, as well as the proportion of participants reporting each frequency of consumption (e.g. 5 days, 6 days, etc.) and/or the mean (SD) or median (IQR) number of days consumed. All descriptive statistics will be reported overall and by intervention group. To investigate whether the number of days differed by intervention group, we will conduct Kruskal-Wallis tests.

**Aim 3 (Symptoms):** The proportion of participants reporting symptoms (any, as well as individual symptoms) during the intervention period will be reported overall (whole intervention period) and by study day for each group. The total number of symptoms reported will be presented in a similar manner. In addition, line graphs will be generated to visualize individual participant trajectories in terms of the number of symptoms reported each day and response/non-response to the daily surveys, and will be color-coded by assigned dose to visualize trends by group. Chi-square or Fisher's Exact test will be used to test whether the frequency of reporting any symptoms differed by assigned dose. ANOVA, Welch's ANOVA or Kruskal-Wallis tests will be used to test whether the total number of reported symptoms differed by dose group.

### Secondary Analyses

**Secondary Aim 1 (willingness to consume):** We will report the proportion of participants who reported that they were willing to continue taking the MLP overall and by dose, and investigate whether the distribution of responses differed by dose group, using Chi-square tests if sample sizes allow.

**Secondary Aim 2 (consumption amount):** Average daily dose consumed on consumption days, total MLP consumption (tsp) during the intervention period, and the proportion consumed of the assigned dose will be presented as mean (SD) or median (IQR). All descriptive statistics will be reported overall and by intervention group. To investigate whether the proportion of assigned dose consumed differed by dose group, we will conduct one-way ANOVA, Welch's ANOVA or Kruskal-Wallis tests. Line graphs will be generated to visualize individual participant trajectories of the daily amount consumed and response/non-response to the daily surveys.

**Secondary Aim 3 (skin carotenoid score):** We will report baseline and post-intervention distributions of SCS by dose group as mean (SD) or median (IQR). To determine whether SCS changed after consuming MLP for one week, we will present the distribution of pre-post-intervention changes in SCS as mean (SD) or median (IQR), by dose group. To investigate whether the change in SCS differed by assigned dose, we will perform ANOVA, Welch's ANOVA or Kruskal-Wallis tests of the change in SCS. As a sensitivity analysis, if the model assumptions for linear regression can be met, we will model change in SCS by regressing endline SCS on intervention group, while adjusting for baseline SCS in the following linear regression model: *Endline SCS ~ Dose group + Baseline SCS*.

Reference

1. Lowry R. One-Way Analysis of Variance for Independent Samples. Part 1. In:2002.
2. Morgan CJ. Use of proper statistical techniques for research studies with small samples. *American Journal of Physiology-Lung Cellular and Molecular Physiology*. 2017;313(5):L873-L877.

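### Secondary Aim 3 asks whether the skin carotenoid score rose, but the plan only tabulates the change by dose, with no interval, paired test, pooled estimate or criterion

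*SAP*

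**What the plan says.** Under Study Aims, the SAP words Secondary Aim 3 as "Determine whether skin carotenoid score (SCS) increased after consuming MLP for one week, and whether the change in SCS differed by dose group". These are two questions: a directional within-person one and a between-dose one.

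Under Secondary Analyses, the within-person question is answered as follows: "To determine whether SCS changed after consuming MLP for one week, we will present the distribution of pre-post-intervention changes in SCS as mean (SD"), or as median (IQR), by dose group. The between-dose question gets ANOVA, Welch's ANOVA or Kruskal-Wallis on the change. It also gets a regression: "As a sensitivity analysis, if the model assumptions for linear regression can be met, we will model change in SCS by regressing endline SCS" on dose group and baseline SCS.

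Three other places bear on this:
- Analysis principles names "Classic ANOVA, Welch's ANOVA, or Kruskal-Wallis tests to detect group differences of ordinal, count and continuous variables". It sets the significance level at 0.05 and mentions effect sizes, but names no interval and no paired or one-sample test.
- Secondary Aim 2, in the same section as the SCS analysis, states "All descriptive statistics will be reported overall and by intervention group". The SCS paragraph says only by dose group.
- Study Design and Sample states "We did not include a control group in order to maximize the sample size for the main outcome of interest", which was acceptability.

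**The concern.** The method does not match the question. The aim is to "Determine whether skin carotenoid score (SCS) increased after consuming MLP for one week", and a table of means with SDs, or medians with IQRs, cannot determine that without a measure of uncertainty or a rule for reading it. The wording also moves from a rise in the aim to a change in the analysis section.

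The planned tests do not fill the gap. A test of equal change across doses has as its null hypothesis that the three mean changes are the same, whatever their common value. A rise of equal size at every dose satisfies that null.

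If the plan is followed as written, how a rise is judged will be settled once the data are in view. Showing the change by dose only also splits the sample in three for a question that applies to every participant.

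**Working it through.** **Inputs.** The change is defined in the SAP under Outcomes (day 8 SCS minus baseline SCS, per participant). The 0.05 level is from Analysis principles; its sidedness is not stated, and two-sided is taken here. The SAP gives no sample size, SD or expected change, so there is no figure to reproduce. Results are in SDs of the within-person change, for assumed n per dose of 10, 15, 20 and 30. The pooled figures assume the same SD across all participants.

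**1. Can the planned tests see a common rise?** Simulation with the same true rise of 0.5 SD at every dose (4,000 runs; 600 for the regression), percentage of runs rejecting at 0.05:

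| n per dose | ANOVA on change | Regression, dose test | Pooled paired t-test |
|---|---|---|---|
| 10 | 5% | 4% | 75% |
| 15 | 5% | 6% | 91% |
| 20 | 5% | 6% | 97% |

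With no rise at all, the ANOVA and regression also reject in about 4% to 5% of runs. They cannot tell the two situations apart.

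**2. Precision by dose and pooled.** The 95% CI half-width is t(0.975, m−1)/√m, with m = n by dose and m = 3n pooled. For n = 15: 2.145/√15 = 0.55 by dose, and 2.015/√45 = 0.30 pooled. The smallest mean rise detectable with 80% power comes from the noncentral t distribution.

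| n per dose | Half-width, by dose | Half-width, pooled | Detectable, by dose | Detectable, pooled |
|---|---|---|---|---|
| 10 | 0.72 | 0.37 | 1.00 | 0.53 |
| 15 | 0.55 | 0.30 | 0.78 | 0.43 |
| 20 | 0.47 | 0.26 | 0.66 | 0.37 |
| 30 | 0.37 | 0.21 | 0.53 | 0.30 |

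**3. Could a reader finish the job from the table?** From mean, SD and n, yes, by dose. From median and IQR, no. Two constructed sets of 15 changes show this:
- A: −60, −50, −40, −4, −3, 4, 6, 10, 14, 18, 22, 24, 25, 26, 27
- B: −6, −5, −4.5, −4, −3, 4, 6, 10, 14, 18, 22, 24, 60, 75, 90

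Both have median 10 and IQR −3.5 to 23. The signed-rank test gives p = 0.41 for A and p = 0.02 for B.

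**4. Smaller point: the dose comparison.** With equal variances and correlation ρ between baseline and endline, the variance is 2(1−ρ) for the change score and 1−ρ² after baseline adjustment. The ratio is (1−ρ²)/(2(1−ρ)) = (1+ρ)/2, which is 0.75, 0.85 and 0.95 at assumed ρ of 0.5, 0.7 and 0.9. Take 15 per dose and endline shifts of 0, 0.25 and 0.5 SD of SCS. Power is then 20% for the change score against 25–26% adjusted, 31% against 35–36%, and 76% against 76–78%. Each range spans the simulated and the noncentral F result. The gain is small and may be nil.

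**The case against.** The best reply is that this is the third secondary aim of a study the SAP itself calls a small pilot. Without a control group, describing the pre-post change and leaving it untested is defensible, and a paired p-value could invite the causal reading one wants to avoid. Rewording the aim as a description would then remove the conflict at no cost. That is a fair alternative. It is not what the SAP does, though: the aim and the analysis paragraph both speak of determining an answer, and the other half of the same aim is tested at 0.05. The missing control group limits attribution to the powder, not estimation of the change.

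Other objections stand in part:
- Pooling averages over three doses, so under a dose-response the pooled mean depends on the allocation. By-dose intervals should sit beside it.
- The signed-rank fallback needs symmetric changes if it is to speak about the median. In set A the mean is 1.3 and the median is 10. The plan should say that the Hodges-Lehmann estimate is then the quantity reported.
- Sets A and B are artificial, with three extreme values each, and bear only on the median (IQR) route.
- The change-score comparison of doses is valid under randomisation. Preferring the adjusted model is a matter of precision, not the correction of an error.

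**Conclusion.** The concern holds. Followed exactly, the SAP produces no measure of uncertainty and no rule for the first half of Secondary Aim 3, and its between-dose tests cannot supply one. With 15 per dose, by-dose intervals are nearly twice as wide as the pooled one (0.55/0.30 ≈ 1.8). All sizes rest on assumed n and are in SD units, because the SAP gives neither n nor SD. The logical gap needs no such assumption. It should be fixed, but its reach is limited: the aim is secondary, the between-dose half has a valid test, and no primary aim is touched.

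**What to change.** In Secondary Analyses, Secondary Aim 3:

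- Name one analysis that answers whether SCS rose: the within-person change pooled over the three doses, with a two-sided 95% CI and a paired t-test at 0.05.
- State the fallback in advance. If visual inspection and a normal probability plot of the pooled changes show clear non-normality, use the signed-rank test with a Hodges-Lehmann estimate and 95% CI.
- Report the change by dose with 95% CIs as supportive, without separate tests.
- State that, with no control group, a rise cannot be attributed to the powder.
- Smaller point: make the regression of endline SCS on dose group and baseline SCS the main dose comparison. Keep the change-score tests as the sensitivity analysis, and as the fallback if the regression assumptions fail.

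If only description is intended, reword the aim to describe the change, and still give it overall and by dose with 95% CIs.

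The cost is two or three sentences in the SAP and a few lines of code. No new data or participants are needed.
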